7.4.1.6 Monitoring of Subjects with Adverse Events

AEs are recorded and assessed continuously throughout the trial (see Section 7.4.1.3) and are assessed for final outcome at the End of Trial Visit. All SAEs ongoing at the End of Trial Visit must be monitored and followed up by the Investigator until stabilization or until the outcome is known, unless the subject is documented as “lost to follow-up”. Reasonable attempts to obtain this information must be made and documented. It is also the responsibility of the Investigator to ensure that any necessary additional therapeutic measures and follow-up procedures are performed.

7.4.2 Pregnancy and In Utero Drug Exposure

Only pregnancies considered by the Investigator to be related to trial treatment (for example, resulting from a drug interaction with a contraceptive medication) are considered to be AEs. However, all pregnancies with an estimated conception date during the period defined in Section 7.4.1.3 must be recorded by convention in the AE page/section of the eCRF. The same rule applies to pregnancies in female subjects and to pregnancies in female partners of male subjects. The Investigator must notify the Sponsor/designee in an expedited manner of any pregnancy using the Pregnancy Report Form, which must be transmitted according to the same process as described for SAE reporting in Section 7.4.1.4.

Investigators must actively follow up, document and report on the outcome of all these pregnancies, even if the subjects are withdrawn from the trial.

The Investigator must notify the Sponsor/designee of these outcomes using the Pregnancy Report Form. If an abnormal outcome occurs, the SAE Report Form will be used if the subject sustains an event and the Parent-Child/Fetus Adverse Event Report Form if the child/fetus sustains an event.

Any abnormal outcome must be reported in an expedited manner as described in Section 7.4.1.4, while normal outcomes must be reported within 45 days after delivery.

In the event of a pregnancy in a subject occurring during the course of the trial, the subject must be discontinued from trial medication immediately. The Sponsor/designee must be notified without delay and the subject must be followed as mentioned above.

7.4.3 Clinical Laboratory Assessments

Fasted blood and urine samples will be collected for the clinical laboratory tests (hematology, biochemistry, virology, drugs of abuse, hormones, and urinalysis) following the timing noted in the Schedule of Assessments ([Table 1](#)). Additional laboratory safety examinations during the course of the trial are at the discretion of the Investigator.

All blood and urine samples must be clearly identified and will be worked up and analyzed in Nuvisan's clinical laboratory. Any abnormalities in any of the laboratory parameters will be judged by a physician individually in relation to the reference ranges from the laboratory.

The Sponsor should receive a list of laboratory normal ranges before shipment of the IMP. Any change in laboratory normal ranges during the trial should be forwarded to the Sponsor, including laboratory certificates.

All safety laboratory examinations will be carried out under fasting conditions. Some additional parameters may be routinely analyzed by the laboratory after abnormal findings, or requested by the Investigator, including but not limited to eg microscopic differential blood count, direct bilirubin and creatine phosphokinase myocardium/brain type.

In case of positive findings of blood, protein, nitrite or leucocytes in the urinalysis, a subsidiary microscopic examination of the sediment will be performed.

For all findings with major deviation and/or possible pathological relevance, follow-up examinations will be carried out until the deviation returns to normal or the absence of pathological relevance can be confirmed. If a deviation considered clinically relevant has not returned to a normal or not clinically relevant value when it is checked during the screening laboratory tests, the subject will not be included in the trial. Laboratory abnormalities considered clinically relevant by the Investigator will be reported as AE.

The following parameters will be determined as summarized in [Table 2](#).

The amount of blood sampled in this trial is specified in [Appendix II](#).

Table 2 Clinical Laboratory Evaluations

Biochemistry	Aspartate aminotransferase Alanine aminotransferase Alkaline phosphatase γ-Glutamyl-transferase Lactate dehydrogenase Creatine phosphokinase ^b Amylase Lipase	Bilirubin (total) ^a Cholesterol Triglycerides Uric acid	Sodium Potassium Creatinine Urea Glucose Cystatin C (if applicable)
Hematology	Hematocrit Hemoglobin Red blood cell count Mean corpuscular volume Mean corpuscular hemoglobin Mean corpuscular hemoglobin concentration	Platelet count White blood cell count	White blood cell differentials and absolute counts ^c : Basophils Eosinophils Lymphocytes Monocytes Neutrophils
Urinalysis	pH Nitrite Protein Glucose	Ketone bodies Urobilinogen Bilirubin	Leucocytes Blood Microscopic examination ^d
		Urine pregnancy test, females only	
Urine drug screen	Cocaine Amphetamines Methamphetamines Opiates	Barbiturates Benzodiazepine Methadone Cannabinoids	Tricyclic antidepressants Cotinine Ecstasy
Other tests	Hepatitis B surface antigen Hepatitis B core antibody Hepatitis C antibody HIV1/HIV2 antibodies Follicle stimulating hormone (if applicable) Thyroid stimulating hormone Serum pregnancy test (beta-HCG), females only eGFR ^e Alcohol breath test		

eGFR = estimated glomerular filtration rate, HIV = human immunodeficiency virus, beta-HCG = beta-human chorionic gonadotropin

^a In case of an increased bilirubin (total) the direct bilirubin will be determined.

^b In case of an increased creatine phosphokinase (CK), myocardium/brain type (CK-MB) will be determined; if the ratio of CK/CK-MB is above 6, troponin will be determined as well.

^c In case of abnormal findings, manual differential blood count can be requested by the Investigator.

^d Only if blood, protein, nitrite, or leukocytes are positive on the dipstick.

^e Estimated glomerular filtration rate calculated using the Cockcroft-Gault equation.

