Table 6	Power and Mean n for Declaring Bioequivalence for Individual PK Parameters	49
Table 7	90% Confidence Intervals for Estimated Test/Reference Ratios, n = 12 per Group.....	50

Table of In-Text Figures

Figure 1	Overall Trial Design	20
Figure 2	Design of the Trial Parts	20
Figure 3	Diagram of Two-Stage Adaptive Design	48

List of Abbreviations

AE	Adverse event
AESI	Adverse events of special interest
ALT	Alanine aminotransferase
ALU	Aluminum
AST	Aspartate aminotransferase
AUC	Area under the plasma concentration-time curve
AUC _{0-∞}	Area under the plasma concentration-time curve from time zero (= dosing time) extrapolated to infinity
AUC _{0-t}	Area under the plasma concentration-time curve from time zero (= dosing time) to the last sampling time (t_{last}) at which the concentration is at or above the lower limit of quantification.
AUC _{extra}	The AUC from time t_{last} extrapolated to infinity
AUC _{extra%}	AUC _{extra} / AUC _{0-∞} in percent
beta-HCG	Beta-human chorionic gonadotropine
BMI	Body mass index
CI	Confidence interval
CK-MB	Creatine phosphokinase - myocardium/brain type
CL/f	Apparent total body clearance considering the fraction of dose (f) absorbed
C _{max}	Maximum plasma concentration
c-Met	Mesenchymal-epithelial transition factor
CRO	Contract research organization
CTCAE	Common Terminology Criteria for AEs
CV	Coefficient of variation
ECG	Electrocardiogram
eCRF	Electronic case report form
eGFR	Estimated glomerular filtration rate
EMA	European Medicines Agency
EudraCT	European Union Clinical Trials Register
FDA	Food and Drug Administration
GCP	Good Clinical Practice
GeoMean	Geometric mean

GMR	Geometric Mean Ratio
h	Hour(s)
HCC	Hepatocellular carcinoma
HGF	Hepatocyte growth factor
HIV1/HIV2	Human immunodeficiency virus 1 and 2
IB	Investigator's Brochure
ICF	Informed Consent Form
ICH	International Council for Harmonisation
IEC	Independent Ethics Committee
IMP	Investigational Medicinal Product
LLOQ	Lower limit of quantification
min	Minute(s)
NCI	National Cancer Institute
NSCLC	Non-small cell lung cancer
PGx	Pharmacogenetics
PK	Pharmacokinetics
QTcF	Corrected QT interval according to Fridericia
SAE	Serious adverse event
SAP	Statistical Analysis Plan
SD	Standard deviation
SUSAR	Suspected unexpected serious adverse reactions
T/R	Test/Reference
$t_{1/2}$	Terminal half-life
TEAE	Treatment emergent adverse event
TF1; TF2; TF3	Tablet Formulation 1; Tablet Formulation 2; Tablet Formulation 3

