Part A investigates the bioequivalence of TF3 and TF2 under fasted condition and is designed in 2 stages. If the PK-variability in Stage 1 is larger than initially assumed, the sample size will be re-calculated (with alpha-correction) and additional subjects may be randomized in Stage 2.

Parts B and C investigate the effect of food on the PK of tepotinib after administration of TF2 (Part B) and TF3 (Part C), respectively.

Each trial part has a 2-period, 2-sequence cross-over design. All 3 trial parts may be performed concurrently.

For each subject, the study consists of a screening period (Day -21 to Day -2) and 2 treatment periods, each lasting 21 days. Eligible subjects will be admitted to the clinical unit on Day -1. Subjects who continue to meet the eligibility criteria will be randomized to 1 treatment sequence on Day 1 of Period 1.

In each study period, the subjects will be hospitalized from Day -1 to Day 4 for safety assessments and PK blood sampling and return to the site on Days 5 - 8 for additional PK blood sampling and monitoring of AEs and concomitant medication. Study drug will be administered on Day 1 of each period. An End of Trial Visit will be performed at the end of Period 2 (21 days after dosing in Period 2).

Planned number of subjects:

At least 64 subjects; more subjects may be enrolled in accordance with the adaptive study design (Part A: 40 subjects in Stage 1, additional subjects in Stage 2, if required; Parts B and C: 12 subjects each).

Primary Endpoints:

- Part A: Area under the plasma concentration-time curve (AUC) from time zero (= dosing time) to the last sampling time at which the concentration is at or above the lower limit of quantification (AUC_{0-t}), AUC from time zero extrapolated to infinity ($AUC_{0-\infty}$) and maximum plasma concentration (C_{max}) of tepotinib observed from time zero to 168 h post-dose of each period
- Parts B and C: AUC_{0-t} , $AUC_{0-\infty}$ and C_{max} of tepotinib observed from time zero to 168 h post-dose of each period.

Secondary Endpoints:

- Time to reach C_{max} (t_{max}), terminal half-life ($t_{1/2}$), apparent total body clearance considering the fraction of dose absorbed (CL/f) and apparent volume of distribution during terminal phase (V_z/f) of tepotinib observed from time zero to 168 h post-dose of each period

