7.1.2 Treatment Periods

The subjects willing to participate in the trial will only be included when all Screening examination procedures have demonstrated that all inclusion criteria and none of the exclusion criteria apply. Subjects will be assigned to a random number within the trial prior to the first administration.

For time points and assessments please refer to [Table 1](#) (Parts A, B and C).

Day -1 (Admission)

Subjects will be admitted to the clinic in the morning of Day -1 until completion of the 72 h assessments in the morning of Day 4 of each period.

In each period, the following assessments will be performed:

- Physical examination
- Measurement of vital signs
- 12-lead safety ECG recording
- Blood and urine sampling for safety laboratory assessments
- Pregnancy test (in urine)
- Urine drug screen (including test for cotinine)
- Alcohol breath test
- Assessment of AEs
- Documentation of concomitant medication
- Evaluation of inclusion and exclusion criteria (Period 1 only)

- Blood sampling for PGx (Period 1 only).

Days 1 to 4 (inpatient)

Prior to dosing on Day 1 the following assessments will be done:

- Measurement of vital signs
- 12-lead safety ECG recording
- Blood and urine sampling for safety laboratory assessments
- Pre-dose PK blood sample for determination of tepotinib and its metabolites.

After completion of pre-dose assessments study drug will be administered in the morning of Day 1 of each period as the following:

Part A: Study drug will be administered in both periods in the fasted state together with 240 mL of water.

Parts B and C: Study drug will be administered in one period in a fasted state and in the other period 30 min after start of a standardized high fat, high calorie breakfast, which must be consumed completely within 25 min. The study drug will be administered together with 240 mL of water.

A detailed guidance on dosage and administration is provided in Section [6.2](#).

After dosing the following assessments will be performed at the time points given in the Schedule of Assessments ([Table 1](#)):

- PK blood samples for determination of tepotinib and its metabolites will be taken regularly until 72 h (Day 4) post-dose before discharge (for time points please refer to Table 1)
- Measurement of vital signs and 12-lead safety ECG recordings on Day 1 (2 h and 8 h post-dose), Day 2 and Day 4 before discharge
- Blood and urine sampling for safety laboratory assessments on Day 2 and Day 4 before discharge

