Appendix II Blood Volume Sampled in the Clinical Trial

Blood sample for	Amount per sample (mL)	Number of Scheduled Blood Samples per Subject					Total amount per Subject (mL)
		Screening	Per Period	No. of Periods per Part	End of Trial Visit	Total	
Clinical laboratory tests							
Biochemistry (incl. viral serology, TSH and FSH levels, if applicable)	4.7	1	4 ^a	2	1	10	47.0
Hematology	2.7	1	4 ^a	2	1	10	27.0
PK	2.0		22 ^b	2		44	88.0
PGx	2.0		2 ^c			2	4.0
Total		2	32		2	66	166.0

Note: the number of blood samples may increase above the scheduled number. Blood samples for clinical laboratory follow-up determinations may become necessary. Technical failure of PK/PGx blood drawing may lead the Investigator to decide immediately to repeat a single blood drawing to have a sample.

Maximal blood volume drawn: Estimate per Subject in this Study that will not be exceeded in this planned trial as by experience of the Investigating Institution: **200**

FSH = follicle stimulating hormone, PGx = pharmacogenetics, PK = pharmacokinetics, TSH = thyroid stimulating hormone.

Clinical laboratory (biochemistry and hematology) blood samples:

^a Each period: on Day -1, pre-dose on Day 1, on Day 2 and before discharge on Day 4 = 4 samples;

PK blood samples for determination of tepotinib and its metabolites:

^b Each period: pre-dose, 15, 30, 45, 60, 90 min, and 2, 3, 4, 6, 8, 12, 16, 24, 36, 48, 60, 72, 96, 120, 144 and 168 h post-dose = 22 samples;

PGx blood samples:

^c PGx blood samples of 2 x 2 mL to be drawn on Day 1 of Period 1 at pre-dose = 2 samples.

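### Protocol Table 2, footnote b: the CK/CK-MB trigger for troponin appears inverted, because it fires when CK-MB is a small share of total CK and not when the share is largest

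*Protocol*

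**What the plan says.** Creatine phosphokinase (CK) is in the biochemistry panel of Table 2 in protocol section 7.4.3. Footnote b attaches a reflex rule to it. A raised CK leads to measurement of CK-MB, and the second step reads: "if the ratio of CK/CK-MB is above 6, troponin will be determined as well". The List of Abbreviations defines CK-MB as "Creatine phosphokinase - myocardium/brain type", so it is the isoenzyme named for heart muscle and brain. The footnote gives no unit and no percent sign.

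The body of section 7.4.3 mentions CK-MB as a possible add-on test after an abnormal finding, but without a ratio or cut-off. Troponin appears nowhere else in either document. SAP section 15.3 only refers the reader back to protocol section 7.4.3.

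The same protocol section also has general safeguards: "Any abnormalities in any of the laboratory parameters will be judged by a physician individually". For major or possibly pathological deviations, "follow-up examinations will be carried out until the deviation returns to normal" or until they are shown not to be relevant. Finally, "Additional laboratory safety examinations during the course of the trial are at the discretion of the Investigator".

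**The concern.** The footnote moves from a general muscle enzyme to its myocardial isoenzyme and then to troponin. The natural purpose of such a chain is to ask whether a raised CK may come from the heart, with a larger CK-MB share being the reason to go further. The printed ratio works the other way: for a given CK it falls as CK-MB rises, so requiring it to exceed 6 selects the samples in which CK-MB is a small part of the total.

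At stake is a mandatory reflex test. In a subject with raised CK and a large CK-MB share, the written rule does not order troponin, and someone has to decide to add it. In subjects with a very small CK-MB share, the rule orders a test that the chain gives little reason to run. That second effect is unnecessary testing and not a safety loss.

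**Working it through.** **Inputs.** From footnote b: the rule applies only when CK is raised; the numerator is total CK, the denominator is CK-MB, and the trigger is a ratio above 6. The documents give no CK or CK-MB values, so all values below are illustrative. Results expressed as a share or in U/L assume that both enzymes are reported in the same activity unit.

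**Step 1: rearrange the rule.** CK/CK-MB > 6 is the same as CK-MB < CK/6. In a common unit this is CK-MB/CK < 1/6 = 16.7%.

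**Step 2: switch point in reported values.** The rule fires below CK/6 and stops at or above it:

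- CK 300: 300/6 = 50
- CK 600: 600/6 = 100
- CK 1200: 1200/6 = 200

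The direction does not depend on units. If CK-MB were reported as mass, the 16.7% would not apply, but at a fixed CK the ratio would still fall as CK-MB rises.

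**Step 3: evaluate the printed rule at CK 600 U/L**, next to a rule that fires when CK-MB exceeds 6% of CK.

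| CK-MB share | CK-MB (U/L) | CK/CK-MB | Printed rule (ratio > 6) | CK-MB above 6% of CK |
|---|---|---|---|---|
| 1% | 6 | 100 | troponin | no |
| 5% | 30 | 20 | troponin | no |
| 6% | 36 | 16.7 | troponin | no |
| 7% | 42 | 14.3 | troponin | troponin |
| 10% | 60 | 10 | troponin | troponin |
| 15% | 90 | 6.7 | troponin | troponin |
| 16.7% | 100 | 6.0 | no | troponin |
| 20% | 120 | 5.0 | no | troponin |
| 25% | 150 | 4.0 | no | troponin |
| 40% | 240 | 2.5 | no | troponin |

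The pattern by share is identical at CK 300 and 1200 U/L, because the ratio depends only on the share.

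**Step 4: compare the two rules.** Up to 6% the printed rule orders troponin and the percentage rule does not. Between 6% and 16.7% both order it. From 16.7% upward only the percentage rule orders it. The printed rule thus falls silent exactly where the CK-MB share is largest.

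**Step 5: relative, not absolute.** CK 3000 with CK-MB 300 gives 3000/300 = 10, which fires. CK 300 with CK-MB 60 gives 300/60 = 5, which does not. High and low therefore have to be read relative to total CK.

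**The case against.** The strongest reply is that neither document says which direction was intended. The chain links three tests, but it does not state that a larger CK-MB share should prompt troponin. That step relies on the ordinary meaning of the tests. The slash may also be loose shorthand for a laboratory CK-MB index. This stands as a limit: the documents support saying that the ratio appears inverted, and they do not prove it. It does not rescue the printed text, however. Reading the 6 as a percentage of CK requires turning the ratio round and adding a percent sign, which concedes that the footnote is wrong as printed. A wish to exclude a cardiac source at high ratios would not explain why troponin is left out when the share is greatest.

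A reader might infer that a high CK-MB never triggers troponin. That is too strong: CK 3000 with CK-MB 300 still fires.

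A reader might also infer that cardiac injury would go undetected. The documents do not support that either. Section 7.4.3 keeps individual physician review, follow-up of relevant deviations and discretionary tests. Biochemistry is drawn in "Each period: on Day -1, pre-dose on Day 1, on Day 2 and before discharge on Day 4 = 4 samples" (Appendix II), and Table 1 schedules a 12-lead ECG at each of those times and at Screening and End of Trial. Section 7.1.2 lists post-dose "12-lead safety ECG recordings on Day 1 (2 h and 8 h post-dose), Day 2 and Day 4 before discharge". Protocol section 3 reports no clinically significant laboratory or ECG findings in 79 healthy subjects, and names lipase and amylase elevation as the only identified risk. These points lower the severity. They do not make the written rule right, because the purpose of a reflex rule is that the next test should not depend on someone choosing to add it.

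**Conclusion.** The point holds in limited form. As printed, footnote b orders troponin when CK-MB is below one sixth of total CK and gives no automatic order at or above that level, so relative to total CK it runs against its own chain. That much is arithmetic and does not depend on units. Two things are assumptions: that a larger CK-MB share was meant to prompt troponin, and that both enzymes share an activity unit, which is needed for the 16.7% figure.

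The loss is confined to automatic ordering in samples with raised CK and a CK-MB share of 16.7% or more (same unit). The documents give no rate for raised CK or for such shares, so no number of affected subjects can be stated. No PK parameter, sample size, alpha level or bioequivalence conclusion is touched. Severity: consider.

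**What to change.** Rewrite the second half of footnote b so that a higher CK-MB share prompts troponin, and state numerator, denominator and unit. For example: *if CK-MB exceeds 6% of total CK (both in the same activity unit), troponin is also measured*. The 6% keeps the printed number but is only an example; the documents do not give the intended cut-off. The site laboratory should confirm the cut-off and unit before the text is changed.

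The cost is one footnote. It adds no visits and no scheduled samples, and no SAP change follows, since SAP section 15.3 only points to protocol section 7.4.3.

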7.4.4 Vital Signs, Physical Examinations, and Other Assessments

7.4.4.1 Vital Signs

Blood pressure (systolic blood pressure [mmHg] and diastolic blood pressure [mmHg]) will be measured per the oscillometric method using an automated device, which also indicates the corresponding pulse rate. Blood pressure and pulse rate will be measured after at least 5 min in a supine position, according to the Schedule of Assessments (see [Table 1](#)).

Body temperature will be measured auricular.

Further vital sign measurements during the trial are at the discretion of the Investigator.

7.4.4.2 Physical Examination

A standard examination will be performed including general appearance, skin, head, neck (including thyroid), eyes, ears, nose, throat, abdomen, as well as neurological, peripheral vascular, musculoskeletal, cardiovascular and pulmonary system.

Physical examination will be scheduled according to the Schedule of Assessments (see Table 1). Further physical examinations during the trial are at the discretion of the Investigator. Any relevant findings are to be recorded on the Medical History form in the eCRF (for findings from the past that occurred prior to ICF signature) or on the AE form in the eCRF (for findings presently occurring; events existing but unresolved prior to drug administration).

7.4.4.3 Electrocardiogram

12-lead ECGs will be recorded according to the Schedule of Assessments (see Table 1) using the ECG system Cardio Perfect®, Welch Allyn. The ECGs will be recorded in a supine position after at least 5 min rest.

Per time-point, the ECG will be stored electronically, printed and reviewed in a timely manner by the Investigator. The original printout will be stored with the subject's source data. Electronic data may be transferred to a central ECG laboratory for central reading and further analysis; these results would be reported separately.

ECG printouts will be signed and dated electronically by the person evaluating the ECG. The ECG will be interpreted by the Investigator (normal/abnormal). For abnormal ECGs, the clinical significance (yes/no) must be judged by the Investigator and the abnormality is to be specified.

Additional ECGs during the trial are at the discretion of the Investigator.

